#### 3.3. NUMBER OF PARTICIPANTS

The researcher will sample of a cohort participants referred to cardiac rehabilitation for phases one and two until adequate numbers have been recruited for pilot trial phase. To calculate the sample size for the study, the researcher used values for the means (M) and standard deviation (SD) based on data from Ma et al. (2014) using the following formula:

Cohen's  $d = M1 - M2 / \sigma$  pooled, where  $\sigma$  pooled =  $\sqrt{(\sigma 12 + \sigma 22) / 2}$ 

M1= means for group  $1 = 29.72\pm3.46$ 

M2= means for group  $2 = 25.30 \pm 3.11$ 

Version 2: 20/05/2016 ----- Page 10 of 42

The resultant value for 2 sided test for alpha = 0.05, with power = 0.80, is a sample size of 9 for each group. Based on the results of the sample size calculation formula, 9 participants with complete data in each group will be required to detect a difference in the means of 4.42 points for the primary outcome at 6 months, assuming a common standard deviation of 3.285, with a power of  $\beta = 80\%$  and a two-sided  $\alpha$  value of 0.05. Assuming up to 50% attrition, a total of 28 participants will be recruited for pilot trial phase.

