The Medication Adherence Self-Efficacy Scale-Revised (MASES-R) consists of 13 items that evaluate an individual's judgment of their ability to adhere to prescribed medications under a variety of challenging situations. Twelve of the items ask about patient confidence in taking medications in specific situations (e.g. busy at home, no symptoms, traveling), and one item addresses confidence in ability to make medication adherence as part of daily routine. Each item is scored on a four point scale, ranging from: 0= Not at all sure, 1= A little sure, 2= Fairly sure, and 3= Extremely sure. A single scale score is presented, the mean of all item scores. Higher scores on the scale indicate higher confidence.

The **Medication Specific Social Support** (MSSS) is an 8-item survey of medication-specific social support to identify how often others may have helped patients with their therapy, with scored for each item ranging from 0 (never) to 4 (very often). A single mean score is presented of medication-specific index of support.

These instruments have demonstrated rigor; see Table 1.

Version 2: 20/05/2016 ----- Page 16 of 42

Table 5: The reliability and validity of the selected study instruments

Concept	Name of Questionnaire	Number of Items	Validity Test	Reliability Test Score
Medication Adherence behaviours & barriers	Medication Adherence Questionnaire (MAQ)	Four-item questionnaire measure medication adherence behaviour specifically, barriers such as; forgetfulness and carelessness, & adverse effects & efficacy	Validated in patients with hypertension, dyslipidaemia, heart failure, and CAD	Cronbach's α= 0.61
Medication Adherence Behaviour (Self- Regulation)	Adherence to Refills and Medications Scale (ARMS)	12-item scale.     The first 8-item medication taking subscale assess correct self-administer prescribed regimen ability.     The next 4-item prescription refill subscale assesses a patient's ability to refill medications on schedule	Validated in patients with CAD & other chronic diseases	Cronbach's α = 0.81
Medication taking beliefs	Belief about Medicine Questionnaire (BaMQ)	●8-item short version.  ● The 4-BaMQ subscales are containing two items each includes: General Harm; General Overuse; Specific Necessity; & Specific Concerns on a five point Likert scale.	BaMQ significantly correlated with other adherence scales: MAQ, Morisky Medication Adherence Scale (MMAQ), & medication adherence rating scale (MARS-5)	Cronbach's α = 0.70

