Pilot trial phase: The researcher will compare the two groups at baseline. Data will be analysed according to intention to treat analysis using statistical methods based on the study hypothesis. The primary outcome will be medication adherence/non-adherence at six months and changes in adherence scores since baseline. Descriptive statistical analyses will be used to illustrate the participants' baseline characteristics. The independent samples t-test will be used to compare the mean medication adherence questionnaire scores (MSSS, MAQ, ARMS, BaMQ, and MASER-R) between the intervention and usual care groups. Paired samples t-test analysis will be used to test within groups differences on medication adherence questionnaire scores (MSSS, MAQ, ARMS, BaMQ, and MASER-R). Logistic regression analysis will be applied to identify variables that significantly influence adherence to medications (i.e. self-efficacy, beliefs, level of confidence, and social support).

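### The pilot-phase logistic regression names four predictors, two from one scale, with at most about two outcome events per predictor at the planned number of completers, so it cannot identify influential variables

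*Protocol*

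**What the plan says.** Section 9 of the protocol (pilot trial phase) plans t-tests on the questionnaire scores and then this model: "Logistic regression analysis will be applied to identify variables that significantly influence adherence to medications (i.e. self-efficacy, beliefs, level of confidence, and social support". The same paragraph defines the trial outcome: "The primary outcome will be medication adherence/non-adherence at six months and changes in adherence scores since baseline".

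Section 5.3.1 describes the only self-efficacy instrument, the 13-item MASES-R: "Twelve of the items ask about patient confidence in taking medications in specific situations". The remaining item also rates confidence. On scoring it says: "A single scale score is presented, the mean of all item scores. Higher scores on the scale indicate higher confidence". No other confidence instrument appears in the instrument list or in the table of instruments.

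On numbers, section 3.3 says: "9 participants with complete data in each group will be required to detect a difference in the means of 4.42 points", and then: "Assuming up to 50% attrition, a total of 28 participants will be recruited for pilot trial phase". Section 9 also plans a logistic regression on predictors of non-adherence in Phase one.

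**The concern.** The model is meant to single out variables that matter for adherence, but it has very few outcome events and a variable list that counts one scale twice. In that situation maximum-likelihood estimates may not exist (separation). Where they do exist they are unstable, and the conclusion depends on which test is read. The predictors are not randomised, so language of influence would claim more than even a well-estimated model could. What is at stake is a table of factors that readers may carry into the design of a later intervention. The between-arm comparison is not affected.

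**Working it through.** **The plan's own figures.** Per arm, n = 2(1.96 + 0.842)² × 3.285² / 4.42² = 169.448 / 19.5364 = 8.67, rounded up to 9. This agrees with section 8. The total of 28 reproduces as 9 × 1.5 = 13.5, rounded up to 14 per arm, times 2.

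**Completers available to the model.**
- At the attrition limit: 28 × 0.5 = 14.
- At the number the power calculation requires: 2 × 9 = 18, which corresponds to 1 − 18/28 = 36% attrition.
- With no loss: 28.

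**Events per predictor.** The rarer outcome category holds at most half the completers.

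| Completers | Most events | Per predictor, 4 named | Per predictor, 3 distinct |
|---|---|---|---|
| 14 | 7 | 1.75 | 2.3 |
| 18 | 9 | 2.25 | 3.0 |
| 28 | 14 | 3.5 | 4.7 |

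These are ceilings, reached only if exactly half are adherent at six months. The protocol gives no expected six-month adherence rate. If 30% is assumed, four predictors have 4.2/4 = 1.05 events each at 14 completers and 5.4/4 = 1.35 at 18.

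**The duplicated predictor.** MASES-R yields one mean score, which section 5.3.1 reads as confidence. If that score supplies both self-efficacy and confidence, the two columns are identical and their coefficients cannot be separated at any sample size. If two different MASES-R subsets were used instead, the terms would probably be highly correlated. The simulation takes a correlation of 0.8 for that case.

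**Simulation.** Settings, all assumed: normal predictors entered jointly; 30% or 50% adherent; log-odds 0 (no effect) or 0.7 per SD (moderate effect); 800 data sets per setting; separation found by linear programming. Percentage of trials separated with moderate effects (30% / 50% adherent):

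| Completers | 4 predictors, one pair r = 0.8 | 3 independent predictors |
|---|---|---|
| 14 | 53 / 49 | 26 / 17 |
| 18 | 31 / 22 | 9 / 6 |
| 28 | 5.6 / 3.5 | 0.7 / 0.3 |

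Tests at the nominal 5% level, at 14 to 18 completers:
- *Wald.* With no effects, under 1% of predictors are flagged. With moderate effects, power per predictor is about 0–3%.
- *Likelihood ratio.* With no effects, each predictor is flagged in about 9.5–14.5% of trials, and at least one of four in about 30–33%. Four independent tests at the correct level would give 1 − 0.95⁴ = 18.5%.

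**Entering predictors one at a time.** This largely removes separation (at most 2% of trials at 30% adherent) but not the imprecision. Under the same moderate effect, Wald power is about 2% at 14 completers and 8–13% at 18. The upper 95% limit for the odds ratio is typically 18–25 times the lower limit at 14, and 12–16 times at 18.

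**The case against.** Several stronger statements are tempting, and the protocol does not support them.

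- *The model will be either unestimable or spuriously significant.* Not so. At 18 completers most simulated trials are estimable, and with Wald tests the usual result is that nothing is significant. Inflated false positives arise with likelihood-ratio tests, and the protocol names no test.
- *Only 14 to 18 people will be analysed.* The 50% is a ceiling on attrition and 18 is a requirement, so up to 28 are possible. At 28 separation is rare. Even then there are at most 3.5 events per predictor.
- *Four terms, two of them perfectly collinear, will be entered.* Joint entry is inferred from a bracketed list. Confidence may be only a loose synonym for self-efficacy, which would leave three predictors. That improves matters without curing them, as the tables show.
- *Trial arm has been left out of the model.* Adjustment terms are commonly left to a statistical analysis plan, and one may exist here. The arms are compared separately by t-test.
- *Everyone is non-adherent at baseline, so there is nothing to model.* Section 5.4 does classify trial entrants that way (criterion 7 in section 4.1 is looser), but six-month status can still vary.

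It can also fairly be said that this is a supplementary analysis in a pilot. That limits its importance but does not justify the stated aim of finding significant influences.

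**Conclusion.** The point holds in a limited form. The protocol itself commits the pilot phase to this regression and to the purpose it is meant to serve. At the planned 14 to 18 completers the ceiling is 1.75 to 2.25 events per named predictor, or 2.3 to 3.0 if the duplicate is dropped. Those ceilings and the single-scale redundancy rest on the protocol alone. The separation and test-error rates rest on the assumed 30–50% adherence, 0.7 log-odds per SD and joint entry, so they show scale and are not forecasts. Under those assumptions the fit fails in roughly a fifth to a half of trials at 14 completers and 6–31% at 18. When it succeeds, it is mostly uninformative (Wald) or anti-conservative (likelihood ratio). It should be changed before analysis, but it does not threaten the comparison of the arms.

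**What to change.** Remove the logistic model from the pilot trial phase. Keep the question about factors in the Phase one regression already planned in section 9, with MASES-R entered once and a penalised fit such as Firth's if events are few. No Phase one sample size is stated, so its adequacy should be checked then and not assumed.

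In the trial phase, report the association of each baseline scale (MASES-R, BaMQ, MSSS) with one named six-month adherence score, adjusted for arm, with 95% confidence intervals. Label it exploratory and drop the language of significant influence.

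The cost is protocol wording and one exploratory table. The remaining intervals will be wide: for an unadjusted correlation near zero, the 95% limits are about ±tanh(1.96/√(n − 3)), which is ±0.53 at 14 completers and ±0.47 at 18, and slightly wider after adjustment for arm.

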#### 10. STORAGE AND ARCHIVING OF STUDY DOCUMENTS

Electronic data will be password protected and kept on the researcher's university laptop as well as the Oxygen Cloud storage platform at UTS which will be provided further security to research data. The completed study questionnaires and materials will be secured at UTS for five years after the completion of the study and they will then be the agreed process destroyed by the Faculty of Health.

#### 11. ETHICAL CONSIDERATIONS

The identities of the participants will be concealed to maintain their privacy and confidentiality (Liamputtong, 2013). Data will be protected by limiting access to the data to the researcher and supervisors only. The researcher will remind participants that their participation in the study will be on voluntary basis and they can withdraw from the study at any time without any consequences.

Version 2: 20/05/2016 ----- Page 24 of 42

#### **APPENDICES**

# **Appendix (A) Medication Adherence Questionnaires**

Situations come up that make it difficult for people to take their medications as prescribed by their doctors. Below is a list of such situations. We want to know your opinion about taking your cardiac medication(s) under each of them. Please indicate your response by checking the box that most closely represents your opinion.

Questions	Yes	No
1. Do you ever forget to take your medicine?		
2. Are you careless at times about taking your medicine?		
3. When you feel better do you sometimes stop taking your medicine?		
4. Sometimes if you feel worse when you take your medicine, do you stop taking it?		

Questions	None of the time	Some of the time	Most the time	All the time
5. How often do you forget to take your medicine				
6. How often do you decide not to take your medicine?				
7. How often do you forget to get prescriptions filled				
8. How often do you run out of medicine?				

Version 2: 20/05/2016 ------ Page 28 of 42

9. How often do you skip a dose of your medicine before you go to the doctor?		
10. How often do you miss taking you medicine when you feel better?		
11. How often do you miss taking your medicine when you feel sick?		
12. How often do you miss taking your medicine when you are careless?		
13. How often do you change the dose of your medicines to suit your needs (like when you take more or less pill than you're supposed to)?		
14. How often do you forget to take your medicine when you are supposed to take it more than once a day?		
15. How often do you put off refilling your medicines because they cost too much money?		
16. How often do you plan ahead and refill your medicines before they run out		

There are no right or wrong answers. For each of the situations listed below, please rate how sure you are that you can take your cardiac medications all of the time.

How confident are you that you can take your cardiac medications:	Not at all sure	A little sure	Fairly sure	Extremely sure
17. When you're busy at home				
18. When there is no one to remind you				
19. When you worry about taking them for the rest of your life				
20. When you do not have any symptoms				
21. When you are with family members				
22. When you are in a public place				
23. When the time to take them is between your meals				
24. When you are travelling				
25. When you take them more than once a day				
26. When you have other medications to take				
27. When you feel well				

Version 2: 20/05/2016 ------ Page 30 of 42

28. If they make you want to urinate while away from home				
Please rate how sure you are that you can carry out the following task:				
29. Make taking your medications part of your routine				

Version 2: 20/05/2016 ------ Page 31 of 42

There are no right or wrong answers. For each of the beliefs listed below, please rate how you agree or disagree about your beliefs of taking medications.

Items	Strongl y Agree	Agree	Uncertai n	Disagree	Strongly Disagree
30. My health, at present, depends on my medicines					
31. My medicines protect me from becoming worse					
32. My medicines disrupt my life					
33. I sometimes worry about long-term effects of my medicines					
34. Doctors use too many medicines					
35. People who take medicines should stop their treatment for a while every now and again					
36. Most medicines are addictive					
37. Medicines do more harm than good					

For the next set of questions, please indicate how often people may have helped you in the various ways described during the PAST THREE MONTHS.

How often has someone in the past three months?

Questions	Never	Rarely	Sometime s	Often	Very often
38. Helped you monitor your symptoms and medication side effects?					
39. Reminded you to take your medications?					
40. Picked up your cardiac medication prescriptions for you?					
41. Helped you understand information about your medications?					
42. Checked in with you about your medications?					
43. Encouraged you to talk to your doctor about your medications when you have questions or problems?					
44. Helped you to believe you can take your medications as prescribed?					
45. Called you specifically to ask how you were doing with your cardiac medications?					

# **Appendix (B) Data Collection Sheet**

Age:	years	Gender:	Male	□ Female	
	DEMOGRAF	PHIC DETAILS:	(Patient	Questions)	
Employme	ent Status:				
Employed		Unemploy	yed but see	eking work	
Retired		Unemploy	ed and not	t seeking work	
Living Arı	rangement: Liv	ves alone □		With partner	
	With Family or	Carer 🗆		With other	
Marital St			lowed c	□ De facto	
Social bac				of birthy	
		agnosed with (H	out a X in	the box for those	that
apply to you		Respiratory diseas	se 🗆	Renal diseases	_
Others (ple	ease list):				

Preferred phone number:		
Email:		
Preferred interview days:	Times:	
Cardiac medications:		
Drug 1: type	- Dosage	
Number of pills to be taken:		- Times
Drug 2: type		
Number of pills to be taken:		- Times
Drug 3: type	- Dosage	
Number of pills to be taken:		- Times
<del></del>		
Drug 4: type	- Dosage	
Number of pills to be taken:		- Times
Drug 5: type	- Dosage	
Number of pills to be taken:		- Times

# Appendix (C): Semi-Structured Interview Guide

Time:	Date:
Location:	Name Symbol:
Introduction:	

Thank you for agreeing to participate in this interview and we will be happy and look forward to your participation till the end of this study.

You are invited to participate in a study being undertaken by [name] (a nursing doctoral student at University of Technology Sydney (UTS)) and supervised by [name] (Prince of Wales Hospital and UTS) and [name] (UTS).

This study looks at how patients with heart disease manage their medications. We are undertaking this study because reports show that for many reasons a significant number of people do not take their medicines in the way they have been prescribed. On average only 50% of medications are taken as prescribed and this is a risk for people health. We want to see if we can help people who have trouble with taking their medications as they have been prescribed.

#### The interview:

- This should take no more than 60 minutes of your time.
- I would like to ask you some questions about your personal experiences with taking medicines as a heart patient in cardiac rehabilitation.
- I am aware that you were referred to this cardiac rehabilitation program after your heart event and you have now been prescribed heart medicines.
- I would like to ask you some questions about your experiences with taking your medicines.

- There are no right or wrong answers. I just want to know what you think. If there are any questions that you prefer not to answer, please feel free to say so. Anything we discuss will be completely confidential.
- I would like to tape record this interview, and then type up what we talk about into a computer. This will be just so I don't miss anything. Your name or any other identifying information will be removed. We will destroy the audiotape once our conversation has been typed up. Anything you say will be combined with other people's interviews and summarized. Your actual words may be used, but you will not be identifiable. Is this agreeable to you?
- You can withdraw at any time from any part of the study without affecting your participation in previously completed parts of the study.

#### **Interview Questions:**

### ➤ What medications or medicines are you currently on?

(**Prompts:** If you can't remember the name, can you remember what they are for? OR – why do you take each of these? Can you tell me what they are for? If not can I remind you of them by reviewing your discharge letter?)

# ➤ Have you taken them today?

(**Prompts:** What time do you usually take each of your medications/ tablets/ pills?)

# How do you feel about your prescribed heart medicines?

(**Prompts:** Are you feel better when you take your medications (For example, have no chest pain, breathing difficulties)? OR – Do you think taking medications makes you feel worse?, If so, why is that?).

# ➤ How do you find taking your prescribed heart medicines? Why?

symptoms, between your meals, traveling, many medication are a lot for you, make you want to urinate).

> Do you find any difficulties with taking your medicines in the way they are prescribed for you? Can you tell me about this?

(**Prompts:** medication name (generic or trade), number of medications, physical disability, forgotten, careless at times, distance, time constraints).

> What strategies do you use to help you take your medications as the way they are prescribed for you?

(**Prompts:** Do you booked a visit with your GP or cardiac specialist to discuss about you medication? You talk with other patients about cardiac medications? Staff explain how you can use your medications?).

- ➤ Is there anything that you think might make it easier for you to take your medicines the way they were prescribed for you? If yes —what are these?

  (Prompts: Specific method you use to remind you taking medicine? Your family member, friends, hospital staff? Your physician, pharmacist, nurse?).
- ➤ Please describe your experience refilling your medications. How easy is it for you to get your medications refilled? If not, tell me why?

(**Prompts:** Did you have any body remind you to go and refill your medicines? Do you have someone who helps you to remember to take your tablets? If yes: Do you rely on them completely to remind you to take your tablets or is it mostly your job to remember and take your tablets?).

Thank you for your time. It is greatly appreciated.

# Appendix (D): An Example of a Motivational Interviewing (MINT) for a Standard Cardiac Patient

Time:	Date:
Location:	Name Symbol:
Introduction:	

Thank you for agreeing to participate in this motivational interview.

You are invited to participate in this trial phase because you have already take part in phase one survey and phase two (interview). All patients who complete the survey and the interview and have medications adherence difficulties and a factors affected their medication adherence will be eligible to participate in this motivational interview.

#### The interview:

- This should take no more than 40 minutes of your time.
- We are going to talk about your personal experiences with taking medicines as a heart patient in cardiac rehabilitation.
- I would like to discuss with you some questions about your experiences with taking your medicines.
- I would like to tape record this interview, and then type up what we talk about into a computer. This will be just so I don't miss anything. Your name or any other identifying information will be removed. We will destroy the audiotape once our conversation has been typed up. Anything you say will be combined with other people's interviews and summarized. Your actual words may be used, but you will not be identifiable. Is this agreeable to you?

